# This time period is defined only for patients treated with open label ramipril but not DB medication (and therefore not in the TS).

For certain efficacy and safety analyses, as well as for laboratory data, measurements will still be considered on-treatment during a follow-up period of e.g.  $X = 7$  days ([see Section 6.7](#)). This will be applied programmatically where needed and not used in trial database set up; for the latter  $X = 0$  will be used.

The efficacy analyses will follow the intention-to-treat (ITT) principle in assigning patients to treatment groups, i.e. patients will be analysed as randomised.

Safety analyses will assign patients to the treatment group as treated. If a patient erroneously receives the wrong trial medication, the patient will be analysed according to the actual trial medication received. In addition, AEs with an onset during the time of the incorrect study treatment will be tabulated and listed separately.

The open-label ramipril run-in period will be labelled as the single treatment arm “OL Ramipril” on relevant outputs.

The first and second double-blind on-treatment periods will be labelled “Empa 25mg” and “Placebo” according to the medication assigned to or taken in that period (note: the additional background ramipril will not, therefore, form part of the double-blind treatment labels).

Demographic and baseline summaries will be presented by assigned treatment sequence, which will be labelled as “Empa25/Pbo” and “Pbo/Empa25” respectively. On these summaries a “Total” column will be presented, which is the sum of the number of patients in the two treatment sequence columns.

In general, on efficacy and safety tables presenting double-blind treatment, a “Total” column will not be added, noting in any case that for a crossover design, “Total” is not the sum of the number of patients displayed under “Empa 25mg” and “Placebo”.

A limited number of exploratory outputs may also display the crossover period as well as the double-blind treatment. For this purpose, the labels used will be “Period 1” and “Period 2”.

## **6.2 IMPORTANT PROTOCOL DEVIATIONS**

There are two aspects that qualify a deviation of the protocol to be important (IPDs):

First, there are PDs that potentially affect the rights or safety of study patients. In this case, the sponsor needs to react immediately to such PDs to prevent recurrence. In most cases, these PDs do not have an impact on whether a patient can be included in an analysis, but they need to be described in the report.

Second, a PD can potentially influence the primary outcome measure for the respective patients in a way that is neither negligible nor in accordance with the study objectives. Therefore, such PDs potentially affect the main study results and conclusions. This second category of IPDs forms the basis for the decision of whether a patient does or does not belong to an analysis set. Further, for a crossover study, certain categories of IPD may affect only one of the two crossover periods, which raises the further possibility of whether the patient should

be retained in the analysis set with data from one of the two crossover periods excluded. Even though this trial has terminated early and there will be no PPS, this second set of IPDs will still be determined.

All other PDs are of minor importance and it is not necessary to describe or list these PDs in the integrated clinical trial report (CTR).

The following table defines the different categories of IPDs. The final column describes which IPDs will be used to exclude patients and/or individual measurements from the analysis sets (see also [Section 6.3](#)).

Table 6.2: 1 Important protocol deviations

Category/Code	Description	Example/Comment
A	Entrance criteria not met	
A1	Target indication not met	
	A1.02	Antidiabetic background therapy not as required for T1D patients
		Inclusion criterion 3 not met No insulin recorded on eCRF for T1D patients Or CSII T1D patients: fewer than 3 months experience of using the pump prior to Visit 1.
	A1.03	No Type 1 Diabetes, Type 2 Diabetes or non-diabetic obesity
		Inclusion criterion 2 not met; no diagnosis of T1D, T2D or obesity.
	A1.05	Time since diagnosis out of range for T1D patients
		Inclusion criterion 2 not met, with a date of diagnosis < 6 months prior to Visit 1 for T1D patients.
A2	Inclusion criteria not met	
	A2.01	HbA1c out of range for T1D and T2D patients
		Inclusion criterion 4 not met  HbA1c <6.3% or > 11.2% at Visit 1 prior to CTP global Amendment 3 for T1D patients. HbA1c <6.5% or > 11.% at Visit 1 after CTP global Amendment 3 for T1D and T2D patients
	A2.02	Age out of range
		Inclusion criterion 6 not met  Age < 18 years at Visit 1.
	A2.03	BMI out of range
		Inclusion criterion 7 not met  BMI <18.5 kg/m  or > 35.0 kg/m  at Visit 1 prior to CTP global Amendment 3 for T1D patients. BMI <18.5 kg/m  at Visit 1 after CTP global Amendment 3 for T1D, T2D or obesity patients.

Table 6.2 : 1 Important protocol deviations (cont.)

Category/Code	Description	Example/Comment
A2.04	eGFR out of range	Inclusion criterion 8 not met  eGFR < 60 mL/min/1.73m  according to CKD-EPI formula derived using central laboratory creatinine value at Visit 1.
A2.07	BP out of range	Inclusion criterion 9 not met  Average systolic/diastolic BP ≤ 90 or 60 mmHg, or average systolic/diastolic BP > 140 or 90 mmHg at Visit 1
A3	Exclusion criteria not met	
A3.02*	Additional background therapy	Exclusion criteria 1, 2, 10 or 13 checked Or any of the following: 
 
• Any SGLT-2 inhibitor within 30 days of Visit 1.
 
• Any antihyperglycaemic drug (e.g. metformin, AGI, GLP-1 analogues, pramlintide, inhaled insulin, pre-mixed insulins etc.) except an SGLT-2 inhibitor, subcutaneous basal or bolus insulin recorded on eCRF within 3 months prior to Visit 1 for T1D patients.
 
• Any concomitant medication at visit 1 known to interfere with the RAAS activity and/or renal function based on investigator judgment (e.g. ACEi, ARBs, aldosterone inhibitors, renin inhibitors etc.).
 
• Weight loss surgery or aggressive diet regimen leading to unstable body weight (based on Investigator's judgment) 3 months prior to Visit 1.
 
• Treatment with anti-obesity drugs 3 months prior to Visit 1 for T1D patients.
 

Table 6.2 : 1 Important protocol deviations (cont.)

Category/Code	Description	Example/Comment
A3.03*	Relevant concomitant diagnoses	Exclusion criteria 3, 4, 5, 6, 8 or 20 checked Or any of the following: 
 
• Severe hypoglycaemia involving coma and/or seizure that required hospitalisation or hypoglycaemia related treatment by an emergency physician or paramedic within 3 months prior to Visit 1*.
 
• Hypoglycaemia unawareness based on Investigator judgment or frequent episodes of unexplained hypoglycaemia (2 or more unexplained episodes within 3 months prior to Visit 1)*.
 
• Occurrence of DKA within 3 months prior to Visit 1 or until Visit 3.
 
• Acute coronary syndrome (non-STEMI, STEMI and unstable angina pectoris), stroke or transient ischaemic attack (TIA) within 3 months prior to Visit 1*.
 
• Diagnosis of brittle diabetes*.
 
• Medical history of cancer within the last 5 years (except resected basal cell carcinoma)*.
 

A3.05*	Blood dyscrasias or any disorder causing haemolysis or unstable red blood cell count	Exclusion criterion 16 checked Or Relevant diagnosis (e.g. malaria, babesiosis, haemolytic anaemia) at Visit 1*.
A3.06	Indication of liver disease	Exclusion criterion 9 checked Or ALT, AST or alkaline phosphate > 3xULN at Visit 1.
A3.07*	Contraindication to any of the drugs in the study regime	Exclusion criterion 11 checked Or Any contraindication to Altace® (ramipril) per local product monograph, including: 
 
• History of angioedema
 
• History of haemodynamically relevant bilateral renal artery stenosis or unilateral renal artery stenosis in a single kidney
 
• History of hypotension or haemodynamically unstable states
 
• History of hypersensitivity reaction to ramipril or to any other ACEi, or to any ingredient in the ramipril formulation
 

Table 6.2 : 1 Important protocol deviations (cont.)

Category/Code	Description	Example/Comment
A3.10*	Treatment with protocol excluded systemic steroids or recent change in thyroid hormone dose	Exclusion criteria 14 or 15 checked Or Treatment with systemic steroids or planned initiation of such therapy at Visit 1 (excluding inhaled or topical use of corticosteroids). Or Change in dose of thyroid hormone within 6 weeks prior to Visit 1 or planned change or initiation of such therapy at Visit 1*.
A3.11*	Intake of other investigational drug in another trial within 30 days prior to intake of study medication in this trial	Exclusion criterion 19 checked Or Intake of another investigational drug in another trial within 30 days prior to Visit 1*. Final decision at DBL meeting based on medical judgment.
A3.12*	Specific exclusion criterion for pre-menopausal women violated	Inclusion criterion 10 or Exclusion criterion 17 checked Or Women who are pregnant, nursing, or who plan to become pregnant whilst in the trial*.
A3.13*	Relevant alcohol or drug abuse and other conditions affecting study compliance	Exclusion criterion 18 checked Or Alcohol or drug abuse within 3 months prior to Visit 1*.
A3.14*	Any other clinical condition unsafe for participation that would jeopardise patient safety while participating in this clinical trial	Exclusion criterion 22 checked Or Any other clinical condition that, based on Investigator's judgment, would jeopardise patient safety during trial participation or would affect the study outcome*. Final decision at DBL meeting based on medical judgment.
A3.22*	Diagnosis of severe gastroparesis	Exclusion criterion 7 checked Or Relevant diagnosis recorded as a baseline condition in the eCRF.
A3.45*	History of Organ Transplant	Exclusion criterion 12 checked Or History of organ transplant, including pancreas, pancreatic islet cells or renal transplant.
A3.46*	Inability to comply with study requirements	Exclusion criterion 21 checked Or Patient not able to understand and comply with study requirements, based on Investigator's judgment*.
B	Informed consent	
B1	Informed consent not available	Inclusion criterion 1 not met Or Informed consent date missing.
B2	Informed consent too late	Informed consent date was after Visit 1 date or after any study related procedure.

Table 6.2 : 1 Important protocol deviations (cont.)

Category/Code	Description	Example/Comment
C	Trial medication and randomisation	
C1	Incorrect trial medication	
	C1.02 Incorrect trial medication taken	Wrong double-blind medication taken (different medication than the patient was allocated to for that period was taken, i.e. drug kit recorded in eCRF is from a different treatment group than the drug kit assigned by IRT).  Can only be judged after DBL as requires unblinding information.
	C1.03* Incorrect background medication dose taken during run-in	Wrong dosage of ramipril dosage consistently taken during run-in period.  Final decision at DBL meeting based on medical judgment.
	C1.04* Incorrect background medication dose taken after randomisation	Wrong dosage of ramipril dosage consistently taken during a treatment period following randomisation.  Final decision at DBL meeting based on medical judgment.
C2	Randomisation not followed	
	C2.01 Treated without randomisation	Patient treated by double-blind medication according to eCRF, but not randomised according to IRT.
C3	Non-compliance	
	C3.01 Non-compliance with randomized study drug intake	Compliance for empagliflozin or placebo over one or both 4 week on-treatment periods <80% or >120% (single compliance value for each treatment period).
	C3.04 Non-compliance with background medication during run-in period.	Average ramipril compliance outside of 80-120% during run-in period (calculated from two compliance values recorded during this period)
	C3.05 Non-compliance with background medication following randomisation	Ramipril compliance outside of 80-120% during a double-blind treatment period or the washout period
C4	Medication code broken	
	C4.01* Medication code broken without just cause	Medication code broken whilst on-treatment without valid reason*.  Final decision at the DBL meeting based on medical judgment.
D	Concomitant medication	
D2	Prohibited medication use	
	D2.01* Use of prohibited medication during run-in or randomized treatment periods	Review of eCRF for contraindicated drugs*.  Final decision at the DBL meeting based on medical judgment.

Table 6.2 : 1 Important protocol deviations (cont.)

Category/Code	Description	Example/Comment
G3	Other trial specific deviation	
G3.43*	Errors in measurement of randomisation baseline GFR value	Protocol for taking clearance measurements (used to calculate GFR) not followed and likely to cause significant error in measurement of visit 8 value*. e.g. Unsuccessful euglycaemic clamp.  Final decision on measurement exclusion at the DBL meeting based on medical judgment.
G3.44*	Errors in measurement of other GFR value	Protocol for taking clearance measurements (used to calculate GFR) not followed and likely to cause significant error in measurement*. e.g. Unsuccessful euglycaemic clamp.  Final decision on measurement exclusion at the DBL meeting based on medical judgment.
G3.45	Randomisation baseline GFR measured outside of visit window	Visit 8 GFR measurement taken < 14 days after start of first intake of ramipril
G3.46	Treatment period GFR measured outside of visit window	GFR measurement taken < 14 days after start of treatment period
G3.47	Insufficient washout	The washout period was < 14 days.

\*Manual IPD (e.g. IPD that is too complex to program or cannot be detected through the data stored in the trial database). Some IPDs may need a combination of manual and programmed checks.

### 6.3 PATIENT SETS ANALYSED

Since this study terminated early, there will be no analyses on the protocol defined subgroups of hyperfilterers, non-responders, responders and normofilterers. Instead, all patients will be analysed together, according to the analysis sets defined below:

- **Screened set (SCR):**  
This patient set includes all patients screened for the trial, with informed consent given and who completed at least one screening procedure at Visit 1. This patient set is not specifically defined in CTP.
- **Run-in set (RIS):**  
The run-in set (RIS) includes all patients from the SCR who were treated with at least one dose of study medication (ramipril, empagliflozin, placebo).
- **Randomised set (RIS):**

This patient set includes all patients from the SCR who were randomized to double-blind treatment. This patient set is not specifically defined in CTP.

- Treated set (TS):

The treated set (TS) includes all patients who were randomised and treated with at least one dose of double-blind study medication (empagliflozin, placebo).

- Full analysis set (FAS):

This patient set includes all patients who were randomised and treated with at least one dose of double-blind study medication (empagliflozin, placebo), and who provided a randomisation baseline (visit 8) GFR measurement and at least one post-randomisation GFR measurement.

- Per protocol set (PPS):

There will be no PPS in this study, however, IPDs will still be defined prior to unblinding. IPDs are detailed in [Table 6.2: 1](#).

[Table 6.3: 1](#) below provides an overview of which analysis sets are to be used for the various endpoints and analysis of the endpoints.

Table 6.3: 1 Patient sets analysed

Patient Set	Subgroup	Class of Endpoint			Safety	Demographics
		Primary	Secondary	Further		
FAS	All patients	2° Analyses	2° Analyses			X
TS	All patients			X	X	
RIS	All patients			One endpoint only	X	X

## **6.5 POOLING OF CENTRES**

This section is not applicable, because the study is performed in only one centre.

## **6.6 HANDLING OF MISSING DATA AND OUTLIERS**

Based on the different reasons of patients' data missing for different endpoints, various methods will be used to assess the impact of missing data on the efficacy endpoints of this trial, depending upon the type of the endpoint.

### **6.6.1 Efficacy analysis**

If one of the pair of scheduled GFR measurements (or other similarly recorded data) is missing, the endpoint will be defined as the single remaining non-missing value, as specified in [Section 5.1](#). If both of the scheduled GFR measurements (or other similarly recorded data) are missing, then the endpoint is missing at that visit.

All GFR measurements available on the trial database after data cleaning activities have been completed (or other similarly recorded data) will be assumed to be technically plausible and eligible for use in the analysis, i.e. will not be set to missing programmatically in any cases.

In the event that GFR values (or other similarly recorded data) at a particular visit are outside the relevant visit window specified in [Section 6.7](#), the values will be retained in analysis datasets, but not used in any analysis.

In the event that randomisation baseline GFR is missing, or **both** double-blind treatment period GFR values are missing, such a patient will be excluded from the FAS by definition, and therefore, excluded from all analyses of GFR after 4 weeks of double-blind treatment. Since ramipril is given to lower GFR in the run-in period, under no circumstances will a missing randomisation baseline GFR be imputed by screening baseline GFR, if randomisation baseline GFR is missing after data cleaning activities have been completed.

For all continuous endpoints (including GFR after 4 weeks of double-blind treatment), any patient with only one available value will still be included in the mixed model analyses in which patient is fitted as a random effect (including the primary analysis of GFR). Missing data for one of the crossover periods is implicitly handled in this type of statistical model under the missing at random (MAR) assumption. This also means that all patients in the FAS will be included in the primary analysis of the primary endpoint. Such a patient will be excluded from other analyses in which patient is fitted as a fixed effect. If it is the first crossover period where the missing value occurs, such a patient will also be excluded from any analysis which only uses data from the first double-blind treatment period.

Since only one value per double-blind treatment period is expected for the endpoints in this trial, performing imputations is not needed (e.g. last-observation-carried-forward, LOCF) within treatment periods, and it will not be appropriate to perform imputations across treatment periods.

For binary endpoints, only patients with data from both double-blind treatment periods contribute to the McNemar test statistic. Consequently, patients with missing values for one or both periods are implicitly excluded from this analysis.

Rescue medication is not used in this trial, and therefore there is no need to set missing values following rescue medication use in any analysis.

Any changes to the above (including the handling of any unresolvable but technically implausible GFR values on the trial database) will be documented in the final blinded report planning meeting (BRPM) minutes.

## **6.6.2 Safety and other variables**

Missing safety data will not be replaced.

## **6.6.3 Missing dates and times**

Missing or incomplete AE dates are imputed according to BI standards (see “Handling of missing and incomplete AE dates”) ([2](#)).

If the date of first period double-blind drug administration is missing, but the patient was randomized, the date of first double-blind drug administration will be set to the date of randomisation, unless there is evidence that no first period drug was taken at all (e.g. all

dispensed drug returned unused). If the date of first double-blind drug administration is partially missing with the month and year present, the date of randomisation will be used if it was in the same month, and the first day of the month will be used otherwise.

If the date of second period double-blind drug administration is missing, but the patient was randomized and completed the washout period, the date of second double-blind drug administration will be set to the date of Visit 12, unless there is evidence that no second period drug was taken at all (e.g. all dispensed drug returned unused). If the date of second double-blind drug administration is partially missing with the month and year present, the date of Visit 12 will be used if it was in the same month, and the first day of the month will be used otherwise.

If the date of first open-label ramipril administration is missing, but the patient was confirmed eligible, the date of first open-label ramipril administration will be set to the date of Visit 4, unless there is evidence that no ramipril was taken at all (e.g. all dispensed drug returned unused). If the date of first open-label ramipril administration is partially missing with the month and year present, the date of Visit 4 will be used if it was in the same month, and the first day of the month will be used otherwise.

If the date of a subsequent ramipril dose change is missing but a changed ramipril dose has been recorded (including zero dose), it will be imputed by the date of new dose prescription (or date of dose interruption) by the site if this can be obtained. If this cannot be obtained, no dose change will be assumed. If the date of a subsequent ramipril dose change is partially missing with the month and year present, the first day of the month will be used in the absence of other information.

All missing times of first drug administration will be imputed as 08:00 in the morning.

Missing drug stop dates will be imputed according to the following principles:

- For a missing first period double-blind medication end date, if an End of Treatment (EoT) visit is documented only, then the date of the EoT visit will be used. If a Visit 11 is documented only, or is documented along with an EoT visit or a Visit 15, then the date of Visit 11 will be used.
- If the first period double-blind medication end date is incomplete with the month and the year present, and the EoT visit and Visit 11 are missing, then the first day of the following month will be used.
- For a missing second period double-blind medication end date, if an EoT visit is documented (in addition to Visit 11), then the date of the EoT visit will be used. If a Visit 15 is documented (in addition to Visit 11), then the date of Visit 15 will be used.
- If the second period double-blind medication end date is incomplete with the month and the year present, and the EoT visit and Visit 15 are missing, then the first day of the following month will be used.
- If the patient is lost to follow up, or continues in the trial without the expected visit for imputation being available at all (e.g. Visit 11 is missing, but Visit 12 and/or Visit 15

present), then the date of the previous double-blind drug dispensing visit + longest possible treatment duration based on drug supply at that visit + 1 day will be used.

- If the ramipril end date is missing, then the date of the previous ramipril dispensing visit + longest possible treatment duration based on drug supply at that visit + 1 day will be used.
- If the ramipril end date is incomplete with the month and year present, then the first day of the following month will be used.
- If a patient died during the course of the trial and no additional information about drug stop date(s) is (are) available, then the date of death will be used as drug stop date(s) assuming that the patient took the medication(s) until the day of death.
- All other cases need to be assessed by the trial team on an individual basis, trying to use the points above as guidance.

If only the year of birth is known, the day and month of birth will be imputed as 01 January.

For partial start and stop dates for concomitant therapies (CT) the following derivations will be used to impute 'worst case' values:

- If the day of the end date is missing then the end date is set to last day of the month.
- If the day and month of the end date are missing then end date is set to 31 December of the year.
- If the day of the start date is missing the start date is set to first day of the month.
- If the day and month of the start date are missing then the start date is set to 01 January of the year.

For other incomplete date information the midpoint of the possible interval will be used. If only the year is present, the day and month will be imputed as 01 July. If year and month is present the day will be imputed as 15. If the year is missing, the date will be considered missing.

All other cases need to be assessed by the trial team on an individual basis, using the above points as guidance.

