### **5.1 PRIMARY ENDPOINT**

The primary endpoint is GFR under euglycaemic conditions after 4 weeks of double-blind treatment (either empagliflozin or placebo added to ramipril).

GFR is measured in units of mL/min/1.73m^2 (=mL•min•1.73m^-2). GFR will be calculated by the local laboratory using the inulin clearance method and then entered by the study site onto the electronic case report form (eCRF). The required euglycaemic conditions are those imposed by the clamp used in the trial.

Inulin method for post baseline visits: Two clearance measurements are taken in the derivation of each GFR reading, scheduled at 90 minutes and 120 minutes after the start of infusion respectively. The mean of the pair of GFR measurements at the relevant 4-week visits (visits 11 and 15) will be calculated and used as the primary endpoint value. If only one GFR measurement is available, the primary endpoint will be that single value.

All recorded GFR measurements on the eCRF will be considered eligible for derivation of the primary endpoint and will be included in the FAS analysis. However, any values measured outside of the visit window (see [Table 6.7: 2](#)) will not be used and will therefore not contribute to the primary endpoint derivation.

It will be assumed that any GFR values which are technically implausible or otherwise incorrect will be removed from the trial database during data cleaning prior to analysis.

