## **6.7 BASELINE, TIME WINDOWS AND CALCULATED VISITS**

To avoid all ambiguity, the term “baseline” should not be used without further qualification. Measurements taken prior to the start of open-label ramipril treatment will be referred to as “screening baseline” (Visit 4). Measurements taken prior to randomisation to one of the two double-blind treatment sequences will be referred to as “randomisation baseline” (Visit 8).

Randomisation baseline will be at visit 8 and prior to intake of any double-blind study drug. If more than one value is recorded at visit 8, the value taken at timepoint -0:05 will be used. These will be referenced to explicitly within [Section 5.3](#) Further endpoints.

Period baseline is the baseline prior to intake of any double-blind study drug, within each of the two cross-over periods. For period 1, this is the same as randomization baseline. For period 2, this is prior to the intake of double-blind study drug in the second sequence of the cross-over. This value has not always been recorded, but is often available for laboratory data.

Time windows for visits will be defined in general relative to the start of the relevant treatment period (and not relative to the start of any treatment or to randomisation). The date and (where relevant) clock time of the first drug administration for that treatment period will be used to determine the visit windows. The notable exception to this is the washout period, which is defined based upon the date and time of the last intake of the first period double-blind medication.

Measurements taken prior to the first intake of any study medication (ramipril, empagliflozin or placebo) will be considered pre-treatment or screening values. Pre-treatment values will be assigned to a visit according to the nominal visit number as recorded on the eCRF or as provided by the laboratory. Measurements taken after the first intake of ramipril but before intake of double-blind medication will be considered run-in or randomization baseline values. Measurements taken after the last intake of the first double-blind medication but before the intake of the second double-blind medication will be considered washout values.

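### Imputing a missing first-dose time as 08:00 can turn a same-day pre-dose safety laboratory sample into an on-treatment value

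*SAP*

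**What the plan says.** SAP Section 6.6.3 fills in a missing first-dose time with one fixed value: "All missing times of first drug administration will be imputed as 08:00 in the morning". When the first-dose date is wholly missing, and nothing shows that the drug was not taken, the same section supplies a date:

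- Ramipril: "the date of first open-label ramipril administration will be set to the date of Visit 4".
- Period 1: "the date of first double-blind drug administration will be set to the date of randomisation".
- Period 2: "the date of second double-blind drug administration will be set to the date of Visit 12".

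Section 6.7 then sorts measurements by order relative to intake. For the screening phase: "Measurements taken prior to the first intake of any study medication (ramipril, empagliflozin or placebo) will be considered pre-treatment or screening values". For the second baseline: "Randomisation baseline will be at visit 8 and prior to intake of any double-blind study drug". Values between the last period 1 dose and the first period 2 dose are washout values, and values after first intake are on-treatment up to the end of the follow-up allowance. On the use of clock time it says: "The date and (where relevant) clock time of the first drug administration for that treatment period will be used to determine the visit windows".

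Section 7.8.2 takes as each safety laboratory baseline the last measurement before the relevant treatment starts. Where a period baseline exists, it replaces the randomisation baseline.

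**The concern.** Baseline visits are the days on which first doses may be taken, and for ramipril and period 2 the date rule puts a missing dose date on the visit itself. A pre-dose sample and the first dose then share a calendar day, and only their clock times separate them. If the dose time is missing, 08:00 stands in for it. Any sample drawn after 08:00 then appears to follow the dose, even if the patient took the drug at the end of the visit. The plan has no rule that protects such samples.

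The laboratory summaries are at stake. The eGFR shift tables in Section 7.8.2.4 use the lowest on-treatment value as well as the last, and the creatinine summary counts doublings on treatment relative to baseline. A misplaced sample affects both sides of these comparisons: it leaves the baseline and joins the on-treatment values.

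**Working it through.** The plan gives no figure to reproduce. The check is of clock and calendar order.

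**1. When the rule misclassifies.** Let t be the sampling time and d the true but unrecorded dose time on the same day, with t < d. The sample is truly pre-dose. With d replaced by 08:00 it is labelled post-dose exactly when t is later than 08:00. Samples drawn before 08:00 are unaffected.

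**2. Can dose and sample share a day?** For ramipril and period 2, yes by the plan's own rule, since a missing dose date becomes the Visit 4 or Visit 12 date. For period 1 the imputed date is that of randomisation, which the SAP does not state to be the Visit 8 date. A recorded dose date with only the time missing can also fall on any of the three visits.

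**3. Would dates alone avoid it?** No. In Table 6.1: 1 run-in ends the day before double-blind treatment starts, and each on-treatment period begins on the date of its first dose. By date alone, a dosing-day sample falls in the on-treatment period. Only clock time or an explicit nominal-visit rule can separate it.

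**4. Effect on laboratory baselines.**
- Visit 12: the sample leaves the period 2 baseline and the randomisation baseline is used instead. By the planned days in Table 6.7: 2, that baseline is 28 (period 1) + 28 (washout) = 56 days older.
- Visit 8: if dosing is that day, the last measurement before treatment becomes an earlier sample.
- Visit 4: the same happens to the screening baseline used for run-in.
- In each case the displaced value becomes eligible as an on-treatment minimum or as evidence of a creatinine doubling.

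**5. Are samples after 08:00 plausible?** The SAP gives no clock times for Visits 4, 8 or 12. The only guide is the clearance schedule, stated for post-baseline visits: "scheduled at 90 minutes and 120 minutes after the start of infusion respectively". If it also applied at Visits 4 and 8 (an assumption):
- 08:00 − 90 min = 06:30 and 08:00 − 120 min = 06:00. The two readings precede the imputed dose only if infusion starts before 06:30 and 06:00 respectively.
- A 07:00 start gives readings at 08:30 and 09:00.

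This shows that visit activity after 08:00 is plausible. It does not time the laboratory draws.

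**6. Effect on visit windows.** A change of dose time within a day moves the anchor by less than 1 day. The planned day is 28 in a window of days 15 to 42, so the margins are 28 − 15 = 13 and 42 − 28 = 14 days. The effect is negligible for visits held near plan.

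**7. How many.** The 31 randomised patients have at most 31 × 3 = 93 first-dose times, so between 0 and 93 could be missing. Patients who entered run-in without being randomised would add ramipril times; their number is not given. One affected patient is 1/31 = 3.2%.

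**The case against.** A reader might infer more: that a Visit 8 GFR labelled post-dose ceases to be a randomisation baseline, so the patient leaves the full analysis set and every GFR model, with screening GFR barred as a substitute. The plan does not support this. Section 6.3 identifies baseline GFR in the full analysis set by nominal Visit 8. Section 6.7 chooses among several Visit 8 values by timepoint label. Section 6.6.1 says recorded GFR values are not set to missing programmatically; the exclusion there concerns a baseline that is absent. The Visit 8 window is anchored on first ramipril, so the double-blind dose time cannot move a reading out of it. The model using screening GFR has been dropped. This part of the objection stands.

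It can also be said that the chain is conditional. It needs a missing time, same-day dosing, a sample after 08:00 and programming that compares clock times. That too stands: the SAP shows neither how often this happens nor that it happens at all. Section 5.3, to which Section 6.7 refers for baselines, is not in the text available for this review and may settle matters for the further endpoints.

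The objection does not remove the laboratory problem. The baselines in Section 7.8.2 are defined as the last value before treatment, not by nominal visit. Section 6.7 assigns values to nominal visits in the screening phase only once they count as pre-treatment. The programmer is left to choose between two readings that can give different baselines.

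**Conclusion.** The concern holds for safety laboratory data. When triggered, the 08:00 rule can give the wrong baseline and admit a pre-dose value to the on-treatment data, and no written rule prevents it. The consequence is confined to descriptive summaries: laboratory changes from baseline, eGFR shift tables and creatinine doublings. In a trial of 31 patients one misplaced value can still be visible in such a table.

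The conclusion assumes that at least one first-dose time is missing on a baseline-visit day, that a sample that day was drawn after 08:00, and that order is decided by clock time. The 3.2% is the weight of one patient, not an estimate of how many are affected. Visit windows are essentially unchanged.

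**What to change.** Amend the sentence in Section 6.6.3. When the time of first intake is missing and the dose date, recorded or imputed, is the day of Visit 4, Visit 8 or Visit 12, count that visit's scheduled pre-dose assessments as before intake. One way is to impute the dose time as just after the last of them. Use 08:00 only when first intake is on a later day.

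The cost is one sentence and a small programming change. No new data are needed.
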